#### Amended Clinical Trial Protocol 07 KY1044/SAR445256-KY1044-CT01/TCD17370 - alomfilimab

10-Nov-2021 Version number: 1

4	Life-threatening consequences; urgent intervention indicated	
 
Introduce thyroid hormones (see hypothyroidism management) if the patient becomes hypothyroid (low free T4/T3, even if TSH is not elevated).
 
Graves' disease should be treated per standard guidelines.
 
	
Note: H	ligh dose corticosteroids (1 mg/kg/c	lay) are not routinely required.	
Grade	CTCAE description	Nanagement	Spacialist rafarral?
1	Fasting glucose >ULN-160 mg/dL (>ULN-8.9 mmol/L)	
 
Type 1 DM with diabetic ketoacidosis: Hold ICI; hospitalize and initiate treatment per standard guidelines.
 
Type 1 DM with the basis of the treatment is a first standard basis of the basi

	
2	Fasting glucose >160-250 mg/dL (>8.9-13.9 mmol/L)	
 
Type 1 DM without diabetic ketoacidosis: Hold ICI for hypergiveemia 2Grade 3. Freat with insulin and continue ICI when patient recovers to Grade 1.
 
Treat with insulin per standard guidelines and restart ICI when patient recovers to Grade 1.
 
	
3	Fasting glucose >250-500 mg/dL (>13.9-27.8 mmol/L); hospitalization indicated	• Provide patient education on diet and lifestyle modification, and blood glucose testing	
4	Fasting glucose >500 mg/dL (>27.8 mmol/L); life-threatening consequences		
DERM	ATOLOGIC		
Maculo	papular rash/dermatitis		
Grade	CTCAE description	Management	Specialist referral?
1	Macules/papules covering <10% BSA with or without symptoms (eg, pruritus, burning, tightness)	
 
Continue ICI
 
Oral antihistamines 
 
Cetirizine/loratidine 10 mg daily (non-sedating); hydroxyzine 10-25 mg QID, or at bedtime
 
 
 
Topical corticosteroids 
 
Class I topical corticosteroid (eg, clobetasol propionate, halobetasol propionate, betamethasone dipropionate cream or ointment) for body; Class V/VI corticosteroid (eg, aclometasone, dipropionate cream) or 0.5%
 
 
 
	

Property of the Sanofi Group - strictly confidential

PAGE 75 OF 217

#### Amended Clinical Trial Protocol 07 KY1044/SAR445256-KY1044-CT01/TCD17370 - alomfilimab

10-Nov-2021 Version number: 1

2 3	Macules/papules covering 10-30% BSA with or without symptoms (eg, pruritus, burning, tightness); limiting instrumental ADL	
 
Continue ICI
 
Non-urgent dermatology referral
 
Oral antihistamines 
 
Cetirizine/loratidine 10 mg daily (non-sedating); hydroxyzine 10-25 mg QID, or at bedtime
 
 
 
Topical corticosteroids 
 
See Grade 1
 
Cetirizine/loratidine 10 mg daily (non-sedating); hydroxyzine 10-25 mg QID, or at bedtime
 
 
 
Hold ICI
 
	✓ ✓
Prurifu	>30% BSA with or without associated symptoms; limiting self-care ADL	
 
Same day dermatology consult
 
Rule out systemic hypersensitivity: CBC with differential, CMP
 
Oral antihistamines 
 
Cetirizine/loratidine 10 mg daily (non-sedating); hydroxyzine 10-25 mg QID, or at bedtime
 
 
 
Systemic corticosteroids
 
Prednisone 0.5-1 mg/kg/day (or equivalent dose of methylprednisolone) until rash resolves to ≤Grade 1
 
	
Grade	Description	Management	Specialist referral?
1	Mild or localized; topical intervention indicated	
 
Emollients with cream or ointment based, fragrance-free products         
 
Class I topical corticosteroid (eg, clobetasol propionate, halobetasol propionate, betamethasone dipropionate) for body; Class V/VI corticosteroid (eg, aclometasone, desonide, hydrocortisone 2.5%) for face, AND oral antihistamines (eg, cetirizine/loratidine 10 mg daily, hydroxyzine 10-25 mg QID, or at bedtime
 
 
 
	
2	Intense or widespread; intermittent; skin changes from scratching (eg, edema, papulation, excoriation, lichenification, oozing/crusts);	
 
Dermatology referral         
 
Class I topical steroid (eg, clobetasol propionate, halobetasol propionate, betamethasone dipropionate) for body; class V/VI steroid (aclometasone, desonide, hydrocortisone 2.5%) for face, AND oral antihistamines (eg, cetirizine/loratidine 10 mg daily, hydroxyzine 10-25 mg QID, or at bedtime
 
 
 
	1

Property of the Sanofi Group - strictly confidential

PAGE 76 OF 217

#### Amended Clinical Trial Protocol 07 KY1044/SAR445256-KY1044-CT01/TCD17370 - alomfilimab

10-Nov-2021 Version number: 1

	oral intervention indicated; limiting instrumental ADL	
 
Oral corticosteroids         
 
Prednisone 0.5-1 mg/kg/day (or equivalent of methylprednisolone) tapered over 2 weeks
 
 
 
		
3	Intense or widespread; constant; limiting self-care ADL or sleep; oral corticosteroid or immunosuppressive therapy indicated	
 
Dermatology referral
 
GABA agonist (eg, pregabalin, gabapentin 100-300 mg TID)
 
Oral corticosteroid 
 
Prednisone 0.5-1 mg/kg/day (or equivalent of methylprednisolone) tapered over 2 weeks
 
 
 
	~	
Notes: 1. Grad *Recom patient c GASTR Colitis	Notes: 1. Grade 4 maculopapular rash/dermatitis is not included in CTCAE *Recommendations provided are based on case reports, series and expert consensus. Use of suggested therapies must be discussed with medical oncology based on individual patient considerations. The impact of these therapies on the anti-tumor immune response and efficacy of cancer treatment is unknown and requires further research. GASTROINTESTINAL			
Grade	CTCAE description	Management	Specialist referral?	
1	Asymptomatic; clinical or diagnostic observations only; intervention not indicated [Grade 1 diarrhea frequency ≤4/day]	
 
Close follow-up within 24-48 h for changes or progression
 
Continue ICI
 
If symptoms persist, start routine stool and blood tests
 
Bland diet advisable during period of acute diarrhea
 
Anti-diarrheal medication is optional but not highly recommended when infectious work-up is negative.
 
		
2	Abdominal pain; mucus or blood in stool [Grade 2 diarrhea frequency 4-6/day]	
 
Hold ICI
 
Outpatient stool and blood work; CRP, ESR, fecal calprotectin, lactoferrin, imaging and endoscopy are optional
 
If diarrhea only, observe for 2-3 days. If no improvement start prednisone 1 mg/kg/day (or equivalent dose of methylprednisolone); anti- diarrheal medication is not recommended
 
If diarrhea and colitis symptoms (abdominal pain ± blood in BM), start prednisone 1 mg/kg/day (or equivalent dose of methylprednisolone) immediately
 
	√ See note 5	

Property of the Sanofi Group - strictly confidential

PAGE 77 OF 217

Amended Clinical Trial Protocol 07 KY1044/SAR445256-KY1044-CT01/TCD17370 - alomfilimab

10-Nov-2021 Version number: 1

		
 
If no improvement in 48 h, increase corticosteroid dose to prednisone 2 mg/kg/day (or equivalent dose of methylprednisolone)
 
		
		
 
If patient improves
 
		
		
 
Taper corticosteroid over 4–6 weeks may be needed
 
		
		
 
Resume ICI when corticosteroid is tapered to ≤10 mg/ day and patient remains symptom-free (Grade ≤1)
 
		
		
 
Continue ICI monotherapy
 
		
		
 
If using combination anti-CTLA-4/ICI immunotherapy, continue ICI agent only
 
		
		
 
ICI dose reduction is not recommended
 
		
		If colitis returns on resuming ICI:		
		• Grade $\leq 2$ : temporarily hold ICI		
		• Grade $\geq$ 3: permanently discontinue ICI		
3 and 4	Grade 3: Severe abdominal pain; change in bowel habits;	• Grade 3: withhold ICI; consider resuming ICI when corticosteroid is tapered to ≤10 mg/day and patient remains symptom-free (Grade ≤1). Consider hospitalization		
	medical intervention indicated;	Grade 4: permanently discontinue ICI and hospitalize		
	diarrhea frequency $\geq 7 \times /day$ ]	Blood and stool infection work-up, inflammatory markers, imaging, endoscopy and GI consult		
	Grade 4: Life-threatening	• Start intravenous prednisone 1-2 mg/kg/day (or equivalent dose of methylprednisolone) immediately		
	intervention indicated urgent	
 
If patient improves, follow instructions for 'If patient improves' for Grade 2
 
		
		• If refractory or no improvement on IV corticosteroid, start prednisone 2 mg/kg/day (or equivalent dose of methylprednisolone) for 3 days		
		• Consider other anti-inflammatory agents eg, infliximab 5 mg/kg, which can be given again after two weeks if a second dose is needed. Vedolizumab may also be used (see Note 4).		
Notes.				
1. CBC	with differential, CMP, ESR and	CRP are recommended before starting immunotherapy, to provide baseline values for comparison over time.		
Despite the association between elevated ESR and CRP and colitis, some insurance companies may not cover these tests.				
2. There is no proven role for prophylactic corticosteroids (budesonide) to prevent GI irAEs. 				
3. Response to infliximab generally occurs within 1–3 days although some patients benefit from a second dose after 2 weeks. Prolonged oral prednisone taper may be required after infliximab administration. Whether infliximab reduces the anti-tumor efficacy of ipilimumab remains unknown. 				

4. Case reports of successful treatment of steroid-dependent immune-related colitis using vedolizumab indicate this may benefit certain patients.

Property of the Sanofi Group - strictly confidential

PAGE 78 OF 217

5. A G	5. A GI consult is warranted in any patient who meets criteria for Grade 2 diarrhea/colitis with negative infectious stool work up.			
Fatigue	Asthenia			
Grade	CTCAE description	Management	Specialist referral?	
3	Fatigue not relieved by rest,	• Dose delay for study treatment-related Grade 3 until resolved to ≤Grade 1		
	limiting self-care ADL	• Discontinue for study treatment-related Grade 3 lasting >7 days or Grade 4		
NEURO	DLOGIC		.	
Enceph	alopathy/Leukoencephalopathy/	Reversible posterior leukoencephalopathy syndrome (PRES)		
Grade	CTCAE description	Management	Specialist referral?	
1	Mild symptoms	Hold ICI and initiate diagnostic work-up		
		Consider permanent discontinuation of ICI if AE worsens or does not improve		
2	Moderate symptoms; limiting instrumental ADL	Hold ICI	1	
		• Start 0.5-1.0 mg/kg/day methylprednisolone equivalents PO or IV once infection has been excluded		
		Consider permanent discontinuation of ICI if AE worsens or does not improve.		
3	Severe symptoms; limiting	Permanently discontinue ICI	1	
	self-care ADL	• Start 1-2 mg/kg/day methylprednisolone equivalents IV and prophylactic antibiotics		
		Consider plasmapheresis if no improvement or symptoms worsen after 3 days		
4	Life-threatening consequences;	Permanently discontinue ICI	1	
	urgent intervention indicated	• Start 1-2 mg/kg/day methylprednisolone equivalents IV and prophylactic antibiotics	and contact	
		Consider plasmapheresis if no improvement or symptoms worsen after 3 days	intensive	
		Contact intensive care unit	care unit	
Notes: CTCAE provides grading criteria for encephalopathy, leukoencephalopathy, and PRES. For all these irAEs, ICI therapy may be continued for Grade 1 irAEs. However, $\geq$ Grade 2 events require an ICI hold, and referral to neurology. For events of $\geq$ Grade 3 severity, ICI should be permanently discontinued, IV corticosteroids administered, and plasmapheresis considered if there is no improvement, or symptoms worsen, after 3 days.				

Amended Clinical Trial Protocol 07 KY1044/SAR445256-KY1044-CT01/TCD17370 - alomfilimab

OPHTHALMOLOGIC			
Uveitis			
Grade	CTCAE description	Management	Specialist referral?
1	Asymptomatic; clinical or diagnostic observations only	
 
Continue ICI
 
Ophthalmology referral within 1 week
 
Start lubrication drops (artificial tears)
 
	✓
2	Anterior uveitis; medical intervention indicated	
 
Hold ICI
 
Ophthalmology referral within 2 days, prior to initiating uveitis treatment
 
Coordinate treatment with ophthalmologist (eg, topical corticosteroids, cycloplegic agents, systemic corticosteroids)
 
	✓
3	Posterior or pan-uveitis (Note)	
 
Permanently discontinue ICI
 
In carefully selected cases it may be appropriate to restart treatment, cautiously, depending on severity, systemic response to immunotherapy and ocular response to topical, local or systemic prednisone (prescribed in coordination with ophthalmologist)
 
URGENT ophthalmology referral (preferably uveitis specialist) prior to initiating treatment. Co-ordinate treatment with specialists
 
Consider systemic corticosteroids in addition to intravitreal/periocular corticosteroids/topical corticosteroid treatment as recommended by ophthalmologist
 
	✓ URGENT
4	Blindness (20/200 or worse) in the affected eye	
 
Permanently discontinue ICI
 
URGENT ophthalmology referral (preferably uveitis specialist) prior to initiating any treatment. Co-ordinate treatment with specialists
 
Consider systemic corticosteroids in addition to intravitreal/periocular corticosteroids/topical corticosteroid treatment as recommended by ophthalmologist
 
	✓ URGENT

Amended Clinical Trial Protocol 07 KY1044/SAR445256-KY1044-CT01/TCD17370 - alomfilimab

Episcleritis (CTCAE scleral disorder)			
Grade	CTCAE description	Management	Specialist referral?
1	Asymptomatic; clinical or diagnostic observations only	
 
Continue ICI
 
Ophthalmology referral within 1 week
 
Start lubrication drops (artificial tears)
 
	J
2	Symptomatic, limiting instrumental ADL; moderate decrease in visual acuity (20/40 or better)	
 
Hold ICI
 
Ophthalmology referral within 2 days, prior to initiating uveitis treatment
 
Coordinate treatment with ophthalmologist (topical steroids, cycloplegic agents, systemic steroids) (See Note)
 
	1
3	Symptomatic, limiting self-care ADL; marked decrease in visual acuity (best corrected visual acuity worse than 20/40 or more than 3 lines of decreased vision from known baseline, up to 20/200);	
 
Permanently discontinue ICI
 
In carefully selected cases it may be appropriate to restart treatment, cautiously, depending on severity, systemic response to immunotherapy and ocular response to topical, local or systemic prednisone (prescribed in coordination with ophthalmologist)
 
URGENT ophthalmology referral (preferably uveitis specialist) prior to initiating treatment (See Note). Co-ordinate treatment with specialists.
 
Consider systemic steroids in addition to intravitreal /periocular steroids /topical steroid treatment as recommended by ophthalmologist
 
	✓ URGENT
4 Note: IN	Blindness (20/200 or worse) in the affected eye IPORTANT: Starting treatment w	
 
Permanently discontinue ICI
 
URGENT ophthalmology referral (preferably uveitis specialist) prior to initiating any treatment (See Note). Co-ordinate treatment with specialists.
 
Consider systemic steroids in addition to intravitreal /periocular steroids /topical steroid treatment as recommended by ophthalmologist
 
vith steroids prior to conducting an eye exam may worsen ocular conditions that are due to infection (eg, her
 
	✓ URGENT petic keratitis/uveitis)
or may mask accurate diagnosis and severity grading when the patient is examined by an ophthalmologist.			

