# 5.2.1 Dosing Regimen

Study treatments	Pharmaceutical form	Route of administration	Dose			Frequency and/or Regimen
			Phase 1	Phase 2 dose assessment	Phase 2	
KY1044	Solution	IV infusion	Escalating doses starting at 0.8 mg	One of two biologically relevant doses	RP2D	Q3W (±3 days)
Atezolizumab	Solution	IV infusion	1200 mg	1200 mg	1200 mg	Q3W (±3 days)

Table 5-1:Dose and Treatment Schedule

Q3W=every three weeks

Patients are to receive KY1044 doses (either as single agent or in combination with atezolizumab) within a 3 days visit window. However, the next dose (as single agent or in combination) may be delayed by up to 7 days to recover from previous Aes.

If doses are not received within this time frame, the dose should be missed and patients should receive the next planned dose according to the schedule on Day 1 of the next cycle. If the patient experiences a related toxicity, the management guidelines provided in Section 5.6 should be followed.

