# 5.3 Treatment Duration

All patients treated with either KY1044 as single agent or in combination with atezolizumab will begin study treatment on Cycle 1 Day 1. Each cycle will consist of 21 days ( $\pm$ 3 days). The next scheduled dose (as single agent or in combination) may be delayed by up to 7 days to recover from previous Aes. If the next dose (as single agent or in combination) cannot be administered within the above mentioned 7-day delay, then the dose should be skipped. Dosing will resume at the scheduled dose or the next lower dose. Dose modifications should follow Section 5.6.

If more than one consecutive dose of KY1044 as single agent or in combination with atezolizumab has to be skipped due to study treatment-related toxicities, then the default position is that IMPs should be permanently discontinued. However, if a patient who misses more than one consecutive dose due to a study treatment-related toxicity experiences clinical benefit, and in the opinion of the Investigator it is in the patient's best interest to remain on study, then the patient may continue treatment after discussion with the Medical Monitor.

A patient may continue treatment with KY1044 as single agent or in combination with atezolizumab within this clinical study, as long as they are continuing to derive benefit from treatment, until the patient experiences unacceptable toxicity or confirmed disease progression per iRECIST. Patients will not be withdrawn from the study due to progressive disease per RECIST 1.1, unless clinically indicated.

Criteria for treatment cessation or patient withdrawal from the study are outlined in Section 8, and management of toxicities is outlined in Section 5.6.

Patients with SD, PR, unconfirmed CR, and unconfirmed progressive disease will continue treatment in additional cycles.

Patients who meet the following criteria will NOT continue treatment in additional cycles:

- Patients who experience unacceptable toxicity.
- Patients with confirmed progressive disease. These patients will enter the Safety follow-up period unless the Investigator considers it to be in the patient's best interest to remain on the study, and after discussion with the Medical Monitor.

• Patients with an unconfirmed progressive disease who show signs of clinical deterioration or toxicity. These patients will enter the Safety follow-up period, and will continue to be followed-up until confirmed progressive disease or initiation of a new treatment.

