# 5.6.2 Follow-up for Toxicities

- The emergence of irAEs may be anticipated based on overall experience in clinical studies with similar immunomodulators.
- An irAE is a clinically important AE of unknown etiology associated with the study • drug exposure. IrAEs are typically low grade and self-limited, often occurring after multiple doses, and most frequently involving the GI tract (diarrhea/colitis), skin (rashes), liver (hepatitis), and endocrine systems (a variety of endocrinopathies) and lung (pneumonitis). Serologic, histologic (tumor sample) and immunological assessments should be performed as deemed appropriate by the Investigator, to verify the immune related nature of the AE, and exclude the neoplastic, infectious or metabolic origin of the AE. Management Algorithms (Table 5-5) have been developed to assist Investigators in assessing and managing the following groups of Aes: Infusion reactions, Hematological, Cardiological, GI, Renal, Pulmonary, Hepatic, Endocrinopathy, Dermatological, Neurological, Ophthalmological, and Rheumatological Aes.
- Patients whose treatment is interrupted or permanently discontinued due to an irAE, AE or clinically significant laboratory value, must be followed-up at least once a week (or more frequently if required by institutional practices, or if clinically indicated) for 4 weeks, and subsequently at approximately 4-week intervals, until resolution or stabilization of the event, whichever comes first. Appropriate clinical experts should be consulted as deemed necessary.
- In case of a suspected irAE, the relevant immunological assessments (eg, rheumatoid factor, anti-deoxyribonucleic acid (DNA) Ab, etc.) should be performed and guidelines as outlined in Table 5-5 (and laboratory assessments Section 6.5.6) should be followed.

All patients must be followed up for irAEs, Aes and SAEs for 90 days following the last dose of KY1044 as single agent or in combination with atezolizumab.

Table 5-5 outlines the follow-up evaluation recommended for selected toxicities. For any irAEs/Aes Grade 1 and/or Grade 2, treatment with KY1044 and atezolizumab (if applicable) should be maintained at the determined dose and schedule, unless otherwise specified in Table 5-5.

10-Nov-2021 Version number: 1

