# Table 5-5: Management of Toxicities Defined as Study Treatment-related Only

Infusion Reaction and Cytokine Release Syndrome (CRS)					
Grade	CTCAE description	Management	Specialist referral		
2	Mild transient reaction; infusion interruption not indicated; intervention not indicated Therapy or infusion interruption indicated but responds promptly to symptomatic treatment (eg, antihistamines, NSAIDS, narcotics, IV fluids); prophylactic medications indicated for ≤24 hours	
 
Drug infusion rate may be decreased, or infusion temporarily interrupted, until resolution of the event
 
Consider reducing the rate of infusion upon re-initiation or subsequent infusions
 
NSAIDs (eg, acetaminophen), antihistamines, opioids, and corticosteroids may be used per Investigator/ institutional guidelines
 
Consider premedication for subsequent infusions per Investigator/ institutional guidelines
 
If CRS is suspected (very high fever and precipitous drops in blood pressure, myalgia, change in mental status) treat with corticosteroids according to local standards (and/or with tocilizumab)
 
Take blood for cytokine measurements immediately after the occurrence of the AE and during treatment
 
			
3	Prolonged (eg, not rapidly responsive to symptomatic medication and/or brief interruption of infusion); recurrence of symptoms following initial improvement; hospitalization indicated for clinical sequelae	
 
Permanently discontinue ICI
 
For severe/life-threatening reactions, manage the patient as clinically appropriate (eg, antihistamines, oxygen, fluids, opioids, corticosteroids, bronchodilators, etc.) per Investigator/institutional guidelines
 
Provide supplemental oxygen, fluids, and other resuscitative measures and/or measures for symptomatic relief (see under Grade 2, above) as needed. Monitor vital signs (eg, BP, HR, respiration, and temperature) every 15 ±5 minutes until resolution
 
	✓ Refer to allergist to prevent future reactions		
4	Life-threatening consequences; urgent intervention indicated				

Amended Clinical Trial Protocol 07 KY1044/SAR445256-KY1044-CT01/TCD17370 - alomfilimab 10-Nov-2021 Version number: 1

HAEMATOLOGICAL					
Grade	CTCAE description	Management	Specialist referral		
Anemia	Anemia				

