4	Life-threatening consequences; urgent intervention indicated	•	Start 1-2 mg/kg/day methylprednisolone equivalents IV, and prophylactic antibiotics	
Nata C	TCAE maggidae anodine anitania fan		inhered motor normanathy and concerns motor normanathy. For all these in A.E., ICI thereasy may be continu	ad for Crada 1 in AEa

Note: CTCAE provides grading criteria for peripheral motor neuropathy and sensory motor neuropathy. For all these irAEs, ICI therapy may be continued for Grade 1 irAEs. However,  $\geq$ Grade 2 events require an ICI hold and referral to neurology. For events of  $\geq$ Grade 3 severity, ICI therapy should be permanently discontinued and IV corticosteroids administered.

ACTH=adrenocorticotropic hormone; ADL=activities of daily living; AE=adverse event; ALT=alanine aminotransferase; ANC=absolute neutrophil count; AST=aspartate transaminase: BID=twice daily; BM-bowel movements; BNP=B-type natriuretic peptide; CBC=complete blood count; CMP=comprehensive metabolic panel; CRP=C-reactive protein; CRS=cytokine release syndrome; CT=computed tomography; CTCAE=Common Terminology Criteria for Adverse Events; DIC=disseminated intravascular coagulation; DLCO=diffusing capacity of the lungs for carbon monoxide; DM=diabetes mellitus; ECG=electrocardiogram; ESR=erythrocyte sedimentation rate; FVC=forced vital capacity; GABA=gamma-aminobutyric acid; GI=gastrointestinal; HC=hydrocortisone; ICI=immune checkpoint inhibitors; ICU=intensive care unit; IV=intravenous; IVIG=intravenous immunoglobulin; LLN=lower limit of normal; MRI=magnetic resonance imaging; NSAIDs=non-steroidal anti-inflammatory drugs; PCP=pneumocystis pneumonia; PLT=platelet; PO=per oral; PRES=posterior leukoencephalopathy syndrome; QID=4 times a day; SITC=Society of Immunotherapy of Cancer; TB=Tuberculosis; TLC=total lung capacity; TNF=tumor necrosis factor; TSH=thyroid stimulating hormone; ULN=upper limit of normal.

- 1. Lee DW, et al. Current concepts in the diagnosis and management of cytokine release syndrome. Blood. 2014;124(2):188-95.
- 2. SERVICES., U.S.D.O.H.A.H., Common Terminology Criteria for Adverse Events (CTCAE) Version 5.0. 27 November 2017. https://ctep.cancer.gov/protocoldevelopment/electronic\_applications/docs/CTCAE\_v5\_Quick\_Reference\_8.5x11.pdf

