8.7.2 Dose Interruption

A dose interruption is defined as any interruption during the administration (infusion) of a dose of study drug. Dose interruptions are recorded on the Exposure KY1044- IV/Infusion Administration or the Exposure Atezolizumab- IV/Infusion Administration CRF pages in time units of minutes, hours, or days.

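### Protocol Table 5-5 tells sites both to hold and that they may continue treatment for Grade 1 encephalopathy, leukoencephalopathy or PRES

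*Protocol*

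**What the plan says.** Protocol Table 5-5 is titled "Management of Toxicities Defined as Study Treatment-related Only". In its Neurologic section, the block for encephalopathy, leukoencephalopathy and PRES has a row for each grade. The Grade 1 row (mild symptoms) reads "Hold ICI and initiate diagnostic work-up", and adds that permanent discontinuation should be considered if the event worsens or fails to improve. The Grade 2 row carries its own separate instruction to hold.

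The note under these rows names the same three conditions. It says "ICI therapy may be continued for Grade 1 irAEs", then requires a hold and neurology referral from Grade 2, and permanent discontinuation from Grade 3.

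The general rule is in Protocol Section 5.6.2: for Grade 1 and Grade 2 events, treatment "should be maintained at the determined dose and schedule, unless otherwise specified in Table 5-5". Section 5.6.1 says its guidelines must be followed, and refers to Table 5-5 for dose modifications due to study-medication toxicity.

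**The concern.** The row and the note differ on whether to dose, at the same grade, for the same events. A site that holds breaches nothing, because the note is only permissive. A site that doses under the note goes against the row. Whether a patient with mild symptoms of possible central neurotoxicity is dosed before the work-up in a first-in-human trial then depends on which line the investigator reads. It is also unclear whether such dosing is a protocol deviation, which Section 7.2.3 requires to be documented.

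The choice also feeds into reported data. Dose intensity is a Phase 1 primary and a Phase 2 secondary tolerability endpoint (Protocol Sections 2.2.1 and 2.2.2), and SAP 10.3.1 tabulates patients with doses not administered.

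**Working it through.** **Text comparison.** The plan states no figure to reproduce on this point, so the first check sets the instructions side by side.

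| Table 5-5 block | Grade 1 row | Note, Grade 1 | Note, Grade 2 and above | Row and note agree at Grade 1? |
|---|---|---|---|---|
| Encephalopathy / leukoencephalopathy / PRES | Hold and work up | May continue | Hold, refer | No |
| Peripheral motor and sensory neuropathy | Continue | May continue | Hold, refer | Yes |

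The second block is a useful comparator. Its note opens "CTCAE provides grading criteria for peripheral motor neuropathy and sensory motor neuropathy" and then uses nearly the same sentences, but there the Grade 1 row says to continue. The mismatch is specific to the encephalopathy block. That pattern would fit wording carried over from one block to the other, though the documents do not prove it.

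**Is there a rule that settles it?** Section 5.6.2 maintains dosing unless the table specifies otherwise. The row does specify otherwise, so the section leans towards the row. It is not decisive, because the note is part of the same table.

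**Size for one affected patient.** The inputs are the Q3W schedule (Protocol Section 5.2.1), the allowance that a next dose "may be delayed by up to 7 days to recover from previous Aes" (same section), and these SAP formulas:

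- Duration in weeks (SAP 8.7.1) = ((last dose date + 21 − first dose date) + 1) / 7
- Absolute dose intensity (SAP 8.7.5) = cumulative dose / duration
- Relative dose intensity (SAP 8.7.5) = cumulative dose / (starting dose × scheduled administrations)

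The illustration assumes 4 or 8 scheduled doses, 21 days apart and otherwise on time, with later doses keeping their 21-day spacing after a delayed one.

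*One dose delayed by 7 days; cumulative dose unchanged:*

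- 4 doses: (63 + 21 + 1)/7 = 85/7 = 12.14 weeks on time, and 92/7 = 13.14 weeks delayed. The ratio of absolute dose intensity is 85/92 = 0.924, a fall of 7.6%.
- 8 doses: (147 + 21 + 1)/7 = 169/7 = 24.14 weeks on time, and 176/7 = 25.14 weeks delayed. The ratio is 169/176 = 0.960, a fall of 4.0%.

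*One mid-course dose skipped; first and last dose dates unchanged:*

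- 4 doses: relative dose intensity 3/4 = 75.0%.
- 8 doses: relative dose intensity 7/8 = 87.5%.

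If dosing continues under the note, relative dose intensity stays at 100%.

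**What does not move.** Protocol Table 5-4 lists no Grade 1 event as a DLT, so the DLT count and the MTD are unaffected, and ORR is not touched. The SAP's dose-interruption count is also unaffected: SAP 8.7.2 defines an interruption as "any interruption during the administration (infusion) of a dose of study drug", and a dose held before infusion is not one.

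**The case against.** The strongest defence is a joint reading: hold for the work-up, then continue if the event stays at Grade 1. This is clinically sensible, but the note states no such sequence. It permits continuation without condition and starts the required hold at Grade 2, so the reading adds a term that is not there.

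A second argument is that the table is guidance. Section 5.6.2 says the algorithms exist to assist investigators and calls the follow-up recommended. Investigator judgement, Medical Monitor access and safety committee review also stand behind it. This softens the consequence, but Section 5.6.1 makes its guidelines mandatory and points to the table for dose modifications, so the conflict still matters.

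Third, the documents do not show which line was intended, and the Grade 1 row has no restart criterion. The first part is correct: choosing the row is a judgement in favour of the safer line. The second is a fair observation about the row as it already stands, and aligning the note does not create it.

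Finally, no trial-level effect is shown. That also stands. The percentages apply to one hypothetical patient, no frequency is available, and the analysis is descriptive.

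**Conclusion.** The concern holds. The Grade 1 row and the note give incompatible dosing instructions for the same events, and no other section settles which applies. Confidence in the mismatch is high because it rests on intact current text.

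The reach is narrow: treatment-related Grade 1 events still ongoing when a Q3W dose falls due, with no frequency given in the documents. For such a patient the dose-intensity effect is 4.0% to 7.6% for a one-week delay, or 12.5 to 25.0 percentage points of relative dose intensity for one skipped dose (100% − 87.5% and 100% − 75.0%), under the assumed 8- or 4-dose courses. No effect on dose finding or the response endpoint is claimed. It should be corrected because it is a dosing rule for possible central neurotoxicity in a first-in-human trial, rather than for its numerical effect.

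**What to change.** Let the Grade 1 row govern. In the note to the encephalopathy block, replace the Grade 1 and Grade 2 sentences with wording such as:

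> At Grade 1, withhold ICI and start the diagnostic work-up. At Grade 2 or above, withhold ICI and refer the patient to neurology.

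Leave the Grade 3 sentence as it is. Leave the peripheral neuropathy note unchanged, since it agrees with its own Grade 1 row.

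The drafting cost is small, but Section 11.4 requires protocol changes to be made by amendment. The clinical cost is an occasional dose delayed by up to 7 days, or skipped, for a mild event. If more than one consecutive dose is skipped for treatment-related toxicity, Section 5.3 says "the default position is that IMPs should be permanently discontinued", unless the patient is benefiting, the investigator judges that staying on study is in the patient's best interest, and continuation is discussed with the Medical Monitor.
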